1.3.7 Criteria for discontinuation

Participants may withdraw at any time by refusing to participate in further assessments or by electing not to continue with pregnancy termination.

We expect loss to follow up for all primary and most secondary outcomes to be rare as most assessments are made on the date of study enrollment. We expect some loss to follow up for the POD1 assessment but will take the following steps to minimize this loss: testing of participant phone numbers at the time of enrollment, providing a reminder about the phone call prior to clinic discharge, agreeing in advance on a convenient time for the follow up phone call, providing participants with the study coordinators phone number, and provision of a gift card by mail after completion.

Patients who experience serious adverse events will be discontinued from the study and allocation may be revealed to ensure appropriate management of medical conditions. An adverse event (AE) is defined as any health-related reaction, effect, toxicity or abnormal laboratory result that a study participant experiences during the course of the study, irrespective of relationship to the study intervention. A serious adverse event (SAE) is defined as any experience that is fatal or life threatening, requires in-patient hospitalization or prolongation of an existing hospitalization, or results in a persistent or significant disability or incapacity.

A data safety monitoring board (DSMB) will be assembled. A DSMB meeting will be triggered by a case of respiratory compromise requiring sedation reversal (naloxone or flumazenil). This board will consist of clinicians and researchers knowledgeable in abortion care, moderate sedation, and gabapentin. The following individuals have agreed to serve on the DSMB:

- [name], Professor of Obstetrics and Gynecology, Division Director of Family Planning, University of California Davis

- [name], MPH, Senior Director of Medical Services, PPFA
- [name], PhD, Professor of Anesthesia/Dean, University of California San Francisco

If triggered to meet, they will review the cumulative data to date and provide advice regarding the safety of continuing, modifying, or discontinuing the study.

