1.3.10 Data analysis

Data analysis will be conducted using Stata. The baseline characteristics of the populations will be described. Intention-to-treat analysis will be performed. Primary continuous outcome (pain score on 100-mm point VAS) for the two treatment groups will be compared using T-tests, and if appropriate, by non-parametric analysis. Secondary outcomes will be compared using Chi-square and T-tests, as applicable. Baseline characteristics will be evaluated for potential interaction or confounding with primary and secondary outcomes. If we observe 5 serious adverse events (SAE) requiring sedation reversal agents before enrolling 50 participants, we will ask the statisticians to unblind allocation and

perform an interval analysis to assess for a relationship between study arm and risk of SAE. Once 50 participants are enrolled, we will ask the same analysis after 6 events occur. These numbers of events are based on the concept that if all of the events are in one treatment arm we would find a statistically significant difference in SAE risk between the arms. For reference, sedation reversal is used in less than 1% of D&Es at both sites. Participants may request that their data not be used for analysis if a request is received prior to analysis as mentioned in the consent form. MedStar Health Research Institute (MHRI) statisticians will be consulted to assist with the analysis as needed.

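### Does the unblinding count in 1.3.10 break down because the SAE definition in 1.3.7 does not name sedation reversal?

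*Combined protocol and SAP*

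**What the plan says.** Section 1.3.10 sets the count: "If we observe 5 serious adverse events (SAE) requiring sedation reversal agents before enrolling 50 participants", statisticians are to unblind and "perform an interval analysis to assess for a relationship between study arm and risk of SAE". It continues: "Once 50 participants are enrolled, we will ask the same analysis after 6 events occur". The reasoning given is "These numbers of events are based on the concept that if all of the events are in one treatment arm" the difference would be statistically significant. For context it adds that "sedation reversal is used in less than 1% of D&Es at both sites".

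Section 1.3.7 gives the definition: "A serious adverse event (SAE) is defined as any experience that is fatal or life threatening", or that involves inpatient or prolonged hospitalization, or lasting or significant disability or incapacity. Reversal is not named. The same section says "Patients who experience serious adverse events will be discontinued from the study and allocation may be revealed" where management requires it, and convenes the DSMB on a single case: "A DSMB meeting will be triggered by a case of respiratory compromise requiring sedation reversal (naloxone or flumazenil"). Once convened, the DSMB reviews the accumulated data. A co-investigator reviews every adverse event, and allocation may be opened for a preliminary analysis if increased risk is suspected.

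Section 1.3.1 lists need for a reversal agent among the monitored adverse events and makes administration of reversal agents a secondary outcome. It limits unblinding to the data analysis or a serious adverse event. Sections 1.3.3 and 1.6 are broader and allow it where an interim assessment is needed or where necessary. Appendix C, chart review item 9, records for each participant whether a reversal agent was given.

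**The concern.** This is the plan's only numerical rule for breaking the blind, and its wording is not uniform. It starts with serious adverse events that needed reversal, goes on to events, ends with SAE risk, and cites a reference rate for all reversals, serious or not. Elsewhere reversal appears as a monitored adverse event and not by name as a serious one.

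Two readings result. On the narrow one, a reversal that meets no seriousness criterion is left out of the count. On the broad one, every reversal counts. That fits the reference rate, but it treats each reversal as serious, which 1.3.7 does not say, and it would bring in that section's provisions on discontinuation and allocation. Two people applying the rule to the same cases could disagree on whether the comparison is due. The protocol itself names over-sedation with gabapentin plus opioids as a concern (1.6), so the rule guards against a foreseen risk.

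**Working it through.** **Inputs.** Triggers of 5 (before 50 enrolled) and 6 (from 50), from 1.3.10. Allocation 1:1, from 1.3.1. Enrollment of 130, so 65 per arm, from 1.3.11. Two-sided alpha of 0.05 for the safety comparison is assumed; 1.3.11 states 0.05 for the primary outcome. The reversal rates and the share f of reversals that count are also assumed, because the documents give only a background rate below 1%.

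**1. The plan's own counts.** With n per arm and all k events in one arm, the two-sided Fisher p-value is 2 × C(n,k) / C(2n,k).

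- 4 against 0, n = 24: p = 0.109.
- 5 against 0, n = 24: 2 × 42,504 / 1,712,304 = 0.0496.
- 5 against 0, n = 25: 2 × 53,130 / 2,118,760 = 0.0502.
- 6 against 0, n = 25: 2 × 177,100 / 15,890,700 = 0.0223.
- 6 against 0, n = 65: p = 0.0277.

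Five is the smallest count that reaches significance just below 50 enrolled. It stops doing so at 50, where the plan moves to six, and six holds to the end of enrollment. The calculation uses only the number of events and the arm sizes, so both counts stand whichever event is meant. They do not depend on the background rate.

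**2. How often the reading would matter.** Let X be the sum of two independent binomials, Bin(65, f × p1) + Bin(65, f × p2), where p1 and p2 are the assumed reversal rates. The chance of at least 6 events in 130 is:

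| Assumed rates | All count (f = 1) | Half count (f = 0.5) |
|---|---|---|
| 1% vs 1% | 0.2% | 0.005% |
| 2% vs 1% | 1.4% | 0.05% |
| 5% vs 0.5% | 15% | 0.9% |
| 10% vs 1% | 73% | 15% |

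The early trigger adds almost nothing at the quoted background: at 1%, the chance of 5 or more in the first 49 is 0.01%. If f is near 1, the two columns coincide.

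**3. What else would have happened by then.** Suppose half of reversals are respiratory, independently of each other. Once 5 reversals have occurred, the chance that none met the DSMB trigger is 0.5^5 = 3.1%. After 6 it is 0.5^6 = 1.6%. So in about 97% to 98% of the trials where the wording could decide anything, the DSMB has already been called to review the accumulated data.

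**4. The passages side by side.** In 1.3.10 the 6 events follow directly from a reference to the same analysis, so they are the same events, and SAE risk is the risk of those events. The all-reversal rate is offered for reference only, and step 1 does not use it. Listing reversal as a monitored adverse event in 1.3.1 does not make it non-serious. Under 1.3.7 every serious event is also an adverse event, and the same list includes transfer to hospital, which may be serious too. The narrow reading is therefore a complete rule with two conditions, one defined in 1.3.7 and the other recorded in Appendix C.

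**The case for a change.** The strongest reply is that a pre-specified count should work without discretion, and the other safeguards rely on it. Allocation may be revealed, or is revealed if necessary. The DSMB trigger is worded differently again, leads to advice, and does not itself set an arm comparison at 5 or 6 events. The two readings also separate in the setting the rule is meant for: at an assumed 10% against 1%, 73% against 15%.

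Part of this stands. No sentence says whether every reversal is serious, and the sections do not describe the event or the conditions for unblinding in the same words. But some judgement on seriousness comes with any SAE definition, and a reversal may well be judged life threatening. The gap of 58 percentage points (73 minus 15) also works both ways: the extra detection on the broad reading is the same thing as extra unblinded looks. Writing in the broad reading would be a choice of trigger, not a correction, and it would sit badly with 1.3.1, which names only serious events as a ground for early unblinding (1.3.3 and 1.3.7 are wider).

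**Conclusion.** The concern is accurate about the wording but does not call for a change. The rule can be applied as written, and its counts of 5 and 6 reproduce and hold under both readings. Near the quoted background rate the choice of reading moves the chance of a triggered comparison by about 0.2 percentage points. Larger differences need reversal rates of 5% to 10% in one arm and a share of serious reversals well below 1. Neither figure is in the documents. In that situation the single-case DSMB trigger and the review of all adverse events would already be active. Every reversal is recorded and, as a secondary outcome, compared by arm at the end whether or not it was classed as serious. This is a gap in definition that the people running the trial can fill sensibly, with no demonstrated gain from rewriting the rule. The conclusion rests on the assumed rates, on f = 0.5 as the illustrative share, and, for the DSMB figure, on half of reversals being respiratory and independent.

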1.3.11 Number of subjects and statistical power

Based on the literature which showed a mean pain score of 3.6 with IV sedation [7], and considering that D&E is expected to be more painful than first-trimester uterine aspiration, we estimate a mean pain score of 45 and a SD of 25 using a 100-point scale for patients in the control group. 30% reduction in pain has been accepted as clinically significant [24]. With 80% power and alpha of 0.05, we will need to include 59 participants in each arm (118 total) to detect a decrease of 13 points on a 100-point scale, approximately 30% reduction in pain. As the primary outcome is assessed on the same day as enrollment, we do not expect significant loss to follow up. Accounting for the possibility of withdrawals or incomplete data, we plan to enroll 130 women. Enrollment of 3-5 patients per week will allow recruitment to be completed in approximately 26-43 weeks (6-10 months).

1.3.12 Study limitations

We are aware that the standard regimen for moderate sedation during second trimester abortion at our facilities (naproxen, tramadol, alprazolam, fentanyl, and midazolam) may provide greater pain relief and sedation than other commonly used regimens and thus may limit our ability to detect an improvement in pain relief. However, our experience is that a significant proportion of women have inadequate pain control despite receiving the standard regimen and therefore they may benefit from gabapentin. The fact that gabapentin has been shown to reduce total narcotic use after major surgery is reassuring. Our sample size limits our ability to detect rare outcomes or complications such as medication adverse reactions.

1.3.13 Duration of project

We anticipate completing the process of IRB approval and training of staff to be complete by the early summer of 2017, at which time enrollment will commence. We expect recruitment and data

collection to last 7-9 months. Data analysis and manuscript preparation will take an additional 2-3 months.

Table 3: Timeline

	2017										2018					
	Mar	Apr	May	Jun	Jul	Aug	Sep	Oct	Nov	Dec	Jan	Feb	Mar	Apr	May	Jun
Material development	■															
IRB Review	■	■	■													
Contracts, Hiring	■	■	■	■												
Staff training				■	■											
Recruitment and data collection					■	■	■	■	■	■	■	■	■			
Data cleaning and analysis													■	■		
Report and manuscript writing														■	■	■

1.5 Links with other projects

None

1.6 Main problems anticipated

The frequency of intraoperative pain assessments will require the study coordinator to remain in the room throughout the procedure and therefore we will limit recruitment to 4 patients per day per site to minimize disruptions to clinic flow. This will also reduce the chance of missing data from

perioperative assessments as a result of the coordinator's unavailability. We also anticipate some loss to follow up at the time of the POD1 assessment; this assessment is a secondary outcome and we are taking steps to minimize loss as described in section 1.3.6. Our final concern relates to the potential for over-sedation with the combination of gabapentin and opioids, which could impact both patient safety and clinic flow if discharge is delayed. Although dose-finding studies have not identified an ideal dose, we suspect that a one-time dose of 600 mg will improve pain control without significantly contributing to sedation. Sedation reversal agents are available at both sites. Adverse events, including respiratory depression, will be monitored, reviewed, and allocation revealed if necessary.

1.7 Expected outcomes of the study and dissemination of findings

This study will contribute to the body of literature on pain control during abortion. It will begin to fill the chasm of evidence on pain control during D&E. This may lead to increased use of gabapentin for family planning procedures. It will also contribute to our knowledge regarding the safety of gabapentin as an adjunct to moderate sedation in an outpatient setting; which may be applicable to other gynecologic procedures as well as other medical and surgical specialties. If found to be effective as an adjunct to moderate sedation, gabapentin may further improve pain control for abortion procedures performed without IV sedation. We expect that adjunct use of gabapentin will improve women's experiences and satisfaction with abortion care.

We plan to present the results of this study at the North American Forum on Family planning or a similar national medical conference. The manuscript will be submitted to *Contraception* or a similar journal for peer review and publication.

2. ETHICAL CONSIDERATIONS

After the proposal is submitted to the Fellowship in Family Planning, we will submit the application for this protocol to MHRI/MWHC IRB. We will also submit the proposal to PPMW for approval through the appropriate channels. Approval through Planned Parenthood Federation of America (PPFA) will also be sought prior to study initiation.

A biostatistician at MHRI will be consulted to provide statistical expertise regarding overall project design, analysis, and results dissemination. She/He will oversee final data analysis to ensure appropriate statistical methods are utilized.

\$271 for mailing gift cards to the patients after follow up call visits.

PPMW will receive \$8,000 for use of their facilities during the study. This is intended to cover the use of a private space for recruitment and enrollment as well as storage needs. It also provides payment for PPMW staff time for medication administration and potential additional monitoring that may be required during the procedure and during the recovery period. Finally, it covers potential impact to health center revenue from effects on patient flow.

Appendix C: Demographics, medical history, chart review

Subject ID:	Date:	Time:	Interviewer:
-------------	-------	-------	--------------

Section one: Demographics

- 1) What is your date of birth? (MM/DD/YYYY): ___ / ___ / _____
- 2) Which of the following BEST describes your racial/ethnic background?
 - White/Caucasian
 - Black or African American
 - Asian
 - Other, Mixed, or Multi-racial
 - Don't know/don't want to answer
- 3) Do you consider yourself to be Hispanic/Latina/Latino?
 - NO
 - YES
- 4) What level of education have you completed?
 - Less than high-school
 - High-school diploma or GED
 - Some college
 - Associates degree or Technical Certification
 - Bachelors degree
 - Masters degree/Doctoral degree
- 5) What is your best estimate of the total yearly income in your household? Include all family members from all sources, before taxes, in [last calendar year]. By "combined family income," I mean your income PLUS the income of all family members living in this household (including cohabitating partners, and armed forces members living at home).
 - <\$10,000
 - \$10,001-25,000
 - \$25,001-50,000
 - \$50,001-75,000
 - \$75,001-100,000
 - >\$100,001
 - Don't know/refused
- 6) What is your insurance type?

- Medicaid/Medicare
- Private insurance
- Other, specify _____
- Uninsured
- Don't know/refused

Section two: Medical history

7) Have you ever been pregnant before?

- NO
- YES → Answer questions a-e below
 - a. Number of miscarriages or ectopic pregnancies _____
 - b. Number of C-sections? _____
 - c. Number of vaginal deliveries? _____
 - d. Number of abortions? ____ (if 0, skip to question 9)
 - e. Number of medical abortions: _____
 - f. Number of surgical abortions: _____

8) Do you have any of the following medical conditions?

		If yes, do you take medication for it?	Name of medication(s):
1. Anxiety	 NO  YES	 NO  YES	
2. Depression	 NO  YES	 NO  YES	
3. Other mental health diagnosis (bipolar, schizophrenia, PTSD): Name of condition(s): _____ _____	 NO  YES	 NO  YES	
4. Medical conditions that may cause chronic pain (fibromyalgia, rheumatoid arthritis, etc.): Name of condition(s): _____	 NO  YES	 NO  YES	

9) Do you currently take any of the following medications?

	Past month	Number of tablets in last month	

		1-9	10-19	20 or more	
1. Opiate Pain medication (including oxycodone, Percocet, oxycontin, methadone, etc.)	 NO  YES				Name: _____
2. Benzodiazepine pain medication (including Xanax, Valium, Ativan, etc.)	 NO  YES				Name: _____

10) Do you, or have you ever, used any of the following substances?

	Past month	Frequency, average during the last month		
1. Cigarettes	 NO  YES	 $\leq 1/2$ PPD	 $>1/2$ to 1 PPD	 > 1 PPD
2. Alcohol	 NO  YES	 < 2 times/week	 2-3 times/week	 ≥ 4 times/week
3. Marijuana	 NO  YES	 < 2 times/week	 2-3 times/week	 ≥ 4 times/week
4. Cocaine/Crack	 NO  YES	 < 2 times/week	 2-3 times/week	 ≥ 4 times/week
5. Heroin	 NO  YES	 < 2 times/week	 2-3 times/week	 ≥ 4 times/week
6. Methamphetamine	 NO  YES	 < 2 times/week	 2-3 times/week	 ≥ 4 times/week
7. Any other illicit drugs to get high	 NO  YES	 < 2 times/week	 2-3 times/week	 ≥ 4 times/week
	Name of drugs: _____			

11) Have you ever been physically or sexually assaulted?

- NO
- YES, Sexually Assaulted
- YES, Physically Assaulted
- YES, Both sexually and physically assaulted

12) Are you having an abortion because of a fetal diagnosis?

- NO
- YES. Please describe: _____

INTRODUCTION TO VISUAL ANALOG SCALE

For these questions, we are going to ask you to make an X on a line. For example, let's say you are asked how much you like Oreo cookies:

How much do you like Oreo cookies? (make an X on the line)

very little _____ very much

You answer the question by making an "X" on the line according to how much you like or dislike Oreo cookies.

If you liked Oreo cookies a lot, then you might make an "X" on the line like so:

very little _____ X _____ very much

If you liked Oreo cookies more than life itself(!), then you might make an "X" on the line like so:

very little _____ X _____ very much

If you hated Oreo cookies, then you might make an "X" like so:

very little X _____ very much

If you thought Oreo cookies were just "OK," then you might make an "X" like so:

very little _____ X _____ very much

The idea is that if you like Oreo cookies, you make an "X" on the line closer to the phrase "very much;" the closer you make the "X," the more you are saying you like Oreo cookies. If you don't like Oreo cookies, you make an "X" on the line closer to the phrase "very little;" the closer you make the "X," the more you are saying you don't like Oreo cookies.

13) How much do you like Oreo cookies? (make an X on the line)

very little _____ very much

14) How much pain do you experience with your menstrual periods? (make an X on the line)

very little _____ very much

15) How much pain do you anticipate having during your procedure? (make an X on the line)

very little _____ very much

16) How much pain you are experiencing at this time? (make an X on the line)

very little _____ very much

Medical Record Review

1) Date of birth (MM/DD/YYYY): ____ / ____ / ____

2) Gestational age: ____ weeks ____ days

3) Height: ____

4) Weight: ____ kg/lbs

5) Medications administered:

Type: (include antibiotics, misoprostol, uterotonics, pain and nausea medication)	Route -Oral -IV -Rectal -Vaginal -Paracervical	Dose	Timing - Pre-op - Intra-op - Post-op	Time	Notes
 Azithromycin	 Oral	 500 mg	 Pre		
 Alprazolam	 Oral	 0.25 mg	 Pre		
 Promethazine	 Oral	 25 mg	 Pre		
 Naproxen	 Oral	 500 mg	 Pre		

6) Time of cervical preparation initiation:

a. Misoprostol: Dose _____ Route: _____ Time: _____ AM / PM

b. Osmotic dilators: Time: _____ AM / PM

i. Number of Dilapan-S: _____

ii. Number of laminaria: _____

7) Time of study medication: _____ AM / PM

- 8) Medications during D&E
- a. Paracervical block agents: please indicate if volume other than 20 mL: _____
 - Lidocaine 1%
 - Vasopressin 4 units
 - Bicarbonate
 - b. Fentanyl total dose: _____ mcg
 - c. Versed total dose: _____ mg
- 9) Was a sedation reversal agent administered (ex: flumazenil, naloxone)?
- Yes
 - No
 - a. If yes, what agent(s) and dose was administered? _____ mg

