1.3.5 Admission procedure

After eligibility has been confirmed and informed consent has been obtained, participants will complete a questionnaire assessing demographic information and medical history (Appendix C). Relevant baseline characteristics including age, gravidity, parity, race, ethnicity, and weeks of gestation will be collected. We will also document pre-existing psychiatric disorders such as depression, anxiety, bipolar disorder and chronic pain syndromes.

She will then be assigned to the next sequentially numbered randomization packet. After initiation of cervical preparation, the participant will consume the study drug from the packet with water or clear juice. Time of administration will be recorded on the patient's chart and will occur at least one hour before the planned procedure. All medications given throughout the clinic experience will be recorded. Method(s) of cervical preparation will be recorded. Antibiotic, anti-emetic, and analgesic administration will be standardized but medications may be adjusted to the need of each woman to accommodate patient characteristics such as allergies and without regard to her enrollment in this study.

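### As printed, the skip at Appendix C item 7d takes women with a prior pregnancy but no prior abortion past question 8, so their psychiatric and chronic-pain history goes unrecorded if the skip is followed

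*Combined protocol and SAP*

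**What the plan says.** Question 7 of Appendix C asks whether the woman has been pregnant before. If yes, she is told "Answer questions a-e below", and a list of sub-items follows that in fact runs to "f. Number of surgical abortions". Item 7d, the number of abortions, carries the instruction "if 0, skip to question 9".

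The next numbered question is "8) Do you have any of the following medical conditions". It has four rows: anxiety, depression, other mental health diagnoses, and "4. Medical conditions that may cause chronic pain (fibromyalgia, rheumatoid arthritis, etc". Each row also asks about medication. The skip lands instead on "9) Do you currently take any of the following medications", which covers only opiates and benzodiazepines.

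Two sections of the protocol bear on the skipped item. Section 1.3.5 (Admission procedure) states: "We will also document pre-existing psychiatric disorders such as depression, anxiety, bipolar disorder and chronic pain syndromes". Section 1.3.10 (Data analysis) states: "Baseline characteristics will be evaluated for potential interaction or confounding with primary and secondary outcomes".

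**The concern.** A zero at 7d should bypass only the breakdown into medical and surgical abortions. Sending the respondent to question 9 removes a whole further question, and it does so according to obstetric history. The form therefore cannot deliver what section 1.3.5 promises for this group of women.

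Psychiatric and chronic-pain history are natural covariates in a trial whose outcomes are pain and anxiety, and section 1.3.10 proposes to examine baseline characteristics for interaction and confounding. If question 8 is blank for a group defined by reproductive history, an analysis that uses it must either leave that group out or guess at the answers. If blanks are entered as no, the conditions are under-counted in exactly that group.

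**Working it through.** The check is mainly a trace of the form, followed by a search for the same information elsewhere.

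**1. Branches of question 7, followed as printed**

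| Obstetric history | Route | Question 8 asked? |
|---|---|---|
| Never pregnant | No skip; runs on to 8 | Yes |
| Prior pregnancy, at least one abortion | 7a to 7f, then 8 | Yes |
| Prior pregnancy, no abortion | 7a to 7d, then 9 | No |

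The third row includes women with earlier births and also women whose only earlier pregnancies were miscarriages or ectopic pregnancies.

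**2. Could another form supply the answers?**

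- The Medical Record Review in Appendix C covers date of birth, gestational age, height, weight, drugs given, cervical preparation and sedation. It has no field for diagnoses.
- Question 9 records opiate and benzodiazepine use but no diagnosis and no other psychiatric medicine.
- Questions 14 to 16 of Appendix C record menstrual, anticipated and current pain, not chronic-pain conditions.
- Appendices D and F, question 5, ask about symptoms since the study medication. Appendix G asks about satisfaction, side effects and willingness to use the method again.
- The anxiety inventory in Appendices D and F measures state anxiety at that moment. Its first use is just before sedation (section 1.3.6). The study drug is taken at least one hour before the planned procedure (section 1.3.5), so this is a post-treatment measure and cannot stand in for baseline history.

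Appendices A and B are not in the public text, so the search covers Appendices C to G. Within those, question 8 is the only source.

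**3. Timing relative to randomization**

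Section 1.3.5 has the questionnaire completed before the next numbered packet is assigned. The skip depends only on obstetric history, so the missingness should not differ by arm.

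**4. Illustrative size**

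The plan gives no figure to reproduce here: the share of participants with a prior pregnancy and no abortion, *s*, is not stated. Planned enrollment is 130 (section 1.3.11). With *s* assumed between 10% and 50%:

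- Missing question 8 = 130 × *s*: 130 × 0.10 = 13, up to 130 × 0.50 = 65.
- Left in an analysis that needs question 8 = 130 − missing: 130 − 13 = 117, down to 130 − 65 = 65.
- If blanks are coded as no, and the true prevalence *p* is the same in skipped and unskipped women (a further assumption), the recorded prevalence is *p* × (1 − *s*). That is 0.90*p* at *s* = 10% and 0.50*p* at *s* = 50%.

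These numbers show scale only. They are not estimates for this trial.

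**The case against.** The strongest reply is that this is a numbering slip whose practical effect is unknown.

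- *The skip may not be followed.* The form has an interviewer field, so staff handle it. The lead-in already miscounts the sub-items, so the numbering is visibly loose and someone might correct the jump on sight. Section 1.3.9 describes both paper collection and REDCap on iPads, and the REDCap branching is not shown. All this stands: the loss is conditional on following the printed form. But a form should not rely on staff departing from it, and uneven departures would make the data harder to interpret.
- *The information may exist elsewhere.* Section 1.3.3 places recruitment after the clinic has documented medical history. This also stands. What is missing is a study field and a step to abstract the history; the history itself may be available.
- *No named analysis depends on question 8.* Section 1.3.10 lists no covariates and specifies no adjusted model, and section 1.3.5 mentions these conditions separately from its main list of baseline characteristics. That limits the consequence, but section 1.3.5 still commits to collecting them.

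A reader might infer more than the documents support: that the data are irretrievably lost for every such woman, that the baseline table as a whole is invalid, or that those dropped would be mostly women who have given birth. The first ignores the two points above. The second ignores that demographics, obstetric history, substance use, assault history, gestational age and anticipated pain are untouched. The third has no figure behind it, since women with only miscarriage or ectopic pregnancy are skipped too.

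**Conclusion.** The inconsistency is certain on the face of the documents: the printed skip at 7d bypasses the only available item that records the conditions section 1.3.5 says will be documented. If it is followed, the question 8 variables are structurally missing by obstetric history.

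The reach is narrow. It covers the question 8 rows of the baseline table, with their medication fields, and any interaction or confounding analysis under section 1.3.10 that uses them. A reader might infer a threat to the trial's main result; there is none. The planned t-test on maximum pain, the unadjusted secondary and safety comparisons and the sample size of 59 per arm do not use question 8.

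The number of women affected cannot be derived from the documents, and the 13 to 65 of 130 above rests wholly on an assumed share. The point should be corrected because the contradiction is clear and the remedy nearly free, not because a large effect has been shown.

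**What to change.** 1. In Appendix C item 7d, change the skip target from question 9 to question 8, so that a zero bypasses only 7e and 7f.
2. In the lead-in to question 7, change the range from a-e to a-f.
3. Check the REDCap branching and make it match.
4. For anyone already taken past question 8, complete it from the clinic's documented medical history where available. Otherwise code it as missing, never as no.

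With the corrected skip, the number bypassing question 8 by design falls to 0 of 130 and the sample size does not change. The cost is a one-digit and a one-letter edit, a branching check, and one short extra question for each affected woman. Chart retrieval is needed only if women have already been enrolled on the printed form.
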